#### 9.3.2 Body Measurements

Body weight (without overcoat and shoes) will be measured at the time points indicated in Table 1 (Dose Escalation) and Table 5 (Expansion) and rounded to the nearest kilogram.

# 9.3.3 Vital Signs

Vital signs, including temperature, blood pressure, and heart rate, should be measured with the subject in a supine or reclined position and recorded. Within each visit, preferably the same equipment shall be used for vital sign measurements. On infusion days, vital signs should be assessed at the time points indicated in Table 3 and Table 7 for Dose Escalation and Expansion, respectively. On non-infusion days, vital signs should be assessed any time during the visit.

# For the Expansion part:

Full vital signs should be collected at Screening only. On subsequent visits (Table 7), collect temperature and blood pressure measurements only.

# 9.3.4 Electrocardiograms

The ECGs will be recorded digitally at the sites by using the standard 12-leads at the time points outlined in Table 2 (Dose Escalation) and Table 6 (Expansion). ECGs will be performed in accordance with the ECG manual issued by the vendor. The digital ECGs will be transmitted from the sites electronically to a central laboratory for a measurement of the cardiac intervals and morphologic assessment by a central cardiologist.

The corrected QT interval (QTc) will be calculated using Fridericia's formula:

$$QTc_F = rac{QT}{\sqrt[3]{rac{RR}{(1s)}}}$$

An overall interpretation of the ECGs will be performed by the investigator, or the investigator may delegate this task to a cardiologist, if applicable. The investigator ECG interpretation must be done using the paper ECG reading from the ECG machine by signing and dating the print out. In case of discrepancy between central and the investigator ECG readings, the central reading will be used for trial analysis purposes.

For the ECG recordings, the subjects must be resting and in a supine or reclined position for at least 10 minutes. Any irregularity observed or occurring during the ECGs (eg, vomiting, cough) should either repeat the ECG or be annotated on the eCRF with the description and time of the occurrence.

If triplicate ECGs are required (see Table 2), they should be performed within 20 minutes but at least 2 minutes apart.

#### 9.3.5 ECOG Performance Status

The ECOG-PS will be assessed by the investigator at the time points indicated in Table 1 (Dose Escalation) and Table 5 (Expansion).

The Screening and C1D1 ECOG-PS must be within 0-1 or the subject cannot receive GEN1044. However, the C1D1 ECOG-PS should not be performed if the Screening ECOG-PS was obtained within the previous 5 days. Performance status will be scored using the ECOG-PS scale index (Table 14).

Version: 4.0

**Table 14 ECOG Performance Status** 

Score	Definition
0	Fully active, able to carry out all normal activity without restriction.
1	Restricted in physically strenuous activity, but ambulatory and able to carry out work of a light or sedentary nature, eg, light housework, office work.
2	Ambulatory and capable of all self-care but unable to carry out any work activities.  Up and about more than 50% of waking hours.
3	Capable of only limited self-care, confined to bed or chair more than 50% of waking hours.
4	Completely disabled. Cannot carry out any self-care. Totally confined to bed or chair.
5	Dead.

Source: (Oken et al., 1982).

# 9.4 Clinical Laboratory Assessments

The tests to be performed are detailed in Table 15; central and local laboratories will be used for analyses. Details on the collections, shipment of samples and reporting of results by the central laboratory are provided to investigators in the laboratory manual.

Laboratory values for biochemistry and hematology must be obtained and reviewed by the investigator prior to each GEN1044 administration to ensure the subject can be dosed according to the dosing instructions defined in the protocol.

Beginning with Cycle 3, local and central laboratory samples should be obtained on Day 1 of each cycle or up to 3 days before Day 1. Every effort should be made to obtain local and central labs on the same day. PSA analysis should be performed by the central laboratory. Hematology, biochemistry, coagulation factors, urine pregnancy, and urinalysis should be performed locally.

For AE reporting of laboratory test abnormalities refer to Section 10.2.2.

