#### 1.3 Schedule of Activities

Table 1 through Table 8 list all of the assessments and indicate with an "X" the evaluations performed by visit.

- Table 1: Visit Evaluation Schedule Dose Escalation Part
- Table 2: PK, ADA and ECG Sampling Dose Escalation Part
- Table 3: Vital Signs Dose Escalation Part
- Table 4: Biomarker Table Dose Escalation Part
- Table 5: Visit Evaluation Schedule Expansion Part
- Table 6: PK, ADA and ECG Sampling Expansion Part
- Table 7: Vital Signs Expansion Part
- Table 8: Biomarker Table Expansion Part

In addition to the fixed visits, it may be necessary to perform some of the assessments at unscheduled time points if deemed clinically necessary by the investigator. All data obtained from these assessments must be supported in the subject's source documentation.

Document Number: TMF-34513

**Table 1** Visit Evaluation Schedule – Dose Escalation Part

Treatment Cycle (C)	Notes	Section Reference	Screening					Cycl	e 1							Cycle	2		
Day (d)/Week (wk)			≤ 28d prior to C1 (1d)	1d	2d	4d	8d	9d	11d	15d	16d	18d	1d	2d	4d	8d	9d	11d	15d
Visit window							+1d			+1d			+2d			+2d			+2d
Informed Consent		13.2.3	X																
Eligibility Criteria		5.1, 5.2	X																
Demographics		9.1.1	X																
Medical History		9.1.2 to 9.1.5	X																
Body weight		9.3.2	X																
Physical Examination	After Screening, perform exam only as indicated by subject's symptoms, AEs, or findings as determined by investigator.	9.3.1	X	X			X			X			X			X			X
Vital Signs	See Table 3 for GEN1044 dosing days. At Unscheduled visit, perform only as indicated by subject's symptoms, AEs, or findings as determined by investigator.	9.3.3	X	X			X			X			X			X			X
ICE Score Assessment	See Table 18.	10.4.2	X	X			X			X			X						
ECG	See Table 2	9.3.4	X																
Radiological Exam/Tumor Imaging	Imaging is calendar based. On-treatment imaging every 6 wks (±7d) for the first 36 wks (calculated from C1D1), then every 12 wks (±7d) until PD, start of new anticancer therapy, consent withdrawn, or death, whichever occurs first.	9.2.1	Xª																
Whole-body Bone Scan	Subjects with prostate cancer. Ontreatment scans every 6 wks (±7d) (or longer per local standards) for the first 24 wks(calculated from C1D1), then every 12 wks (±7d) until PD, start of new anticancer therapy, consent withdrawn, or death, whichever occurs first.	9.2.1	X																

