Physical Examination	After Screening, perform exam only as indicated by subject's symptoms, AEs, or findings as determined by investigator.	9.3.1	X	X	X	X	Xf	Xf	X	X		X
Vital Signs	See Table 3 for GEN1044 dosing days. At Unscheduled visit, perform only as indicated by subject's symptoms, AEs, or findings as determined by investigator.	9.3.3	X	X	X	X	Xf	Xf	X	X		Х
ECG	See Table 2	9.3.4										
Radiological Exam/Tumor Imaging	Imaging is calendar based. On-treatment imaging every 6 wks (±7d) for the first 36 wks (calculated from C1D1), then every 12 wks (±7d) until PD, start of new anti-cancer therapy, consent withdrawn, or death, whichever occurs first.	9.2.1							$X^d$			
Whole-body Bone Scan	Subjects with prostate cancer. Ontreatment scans every 6 wks (+7d) (or longer per local standards) for the first 24 weeks (calculated from C1D1), then every 12 weeks (±7d) until PD, start of new anti-cancer therapy, consent withdrawn, or death, whichever occurs first.	9.2.1							X d			
ECOG-PS	At Unscheduled visit, only if relevant.	9.3.5	X			X			X	X		X
Adverse Events	See footnote "b." Report all AEs from first GEN1044 dose (C1D1) until 30 days after the last GEN1044 dose (ie, Safety Follow-up visit). After SFU, only report suspected GEN1044-related SAEs.	10.1, 10.2	X	X	X	X	Xf	X f	X	X	X	X
Concomitant Medication		6.5, 9.1.4	X	X	X	X	Xf	Xf	X	X		X
Premedication with Corti- costeroids, Antihistamines and Antipyretics	Premedication is mandatory 30 to 120 min prior to first 3 administrations of GEN1044	6.2, 6.5										
GEN1044 Administration		6.3, 6.6	X	X	X	X						

Document Number: TMF-34513

Treatment Cycle (C)	Notes	Section Reference	Cycle	3 to C	ycle 4	Cyc	le 5 to	PDf	Treatment Discontin- uation visit	Safety Follow-up visit	Survival Follow-up	Unscheduled
Day (d)/Week (wk)			1d	8d	15d	1d	8d	15d	-	30d after last dose	Every 12 wk after last dose	
Visit window			+3d	+1d	+3d	+3d	+3d	+3d		+14d	+7d	
End of treatment	Perform Treatment Discontinuation visit as soon as possible after permanent GEN1044 discontinuation	8.1, 8.1.1							X			
Inquire if any new anti-cancer treatment		8.1.2							X	X	X	
Survival follow-up	Perform survival follow-up by telephone, email, or visit.	8.1.3, 9.2.3									X	
LABORATORY ASSESS	MENTS											
Hematology	At Unscheduled visit, only if relevant.	9.4	Xe			Xe			Xe	$X^e$		X
Biochemistry	At Unscheduled visit, only if relevant.	9.4	Xe			Xe			Xe	Xe		X
Coagulation factors	At Unscheduled visit, only if relevant.	9.4							Xe			X

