- e. Starting with C3, obtain labs ≤3 days before D1. Central lab: PSA; local lab: hematology, biochemistry, coagulation factors, urine pregnancy test, and urinalysis.
- f. Subjects in cohorts receiving 1 interim dose will receive: A priming dose on C1D1; an intermediate dose on C1D8; and the first full dose on C1D15. Subjects in cohorts receiving 2 interim doses will receive: A priming dose on C1D1; intermediate doses on C1D8 and C1D15; and the first full dose on C2D1.

Document Number: TMF-34513

Version: 4.0

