# **6.3** Dosages and Administration

Trial treatment should be administered as described in Section 4.2 (Dose Escalation) and Section 4.3 (Expansion) until one or more of the discontinuation criteria in Section 8.1 are met:

- Cycles 1 through 4: Days 1, 8, and 15 (once weekly for a 21-day cycle)
- Cycles 5 and beyond: Day 1 (every 3 weeks for a 21-day cycle)

Refer to the preparation and administration guideline for additional information and stepwise guidance on dosage and administration.

Detailed dose modification guidance is provided in Section 7. Refer to Section 6.5 for information regarding concomitant therapy.

GEN1044 will be administered using IV infusion on Days 1, 8, and 15 of each 3-week (21-day) treatment cycle. GEN1044 will be administered as a fixed dose. In the Dose Escalation part, subjects will be administered GEN1044 according to dose levels outlined in Section 4.2. In the Expansion part, subjects will be administered GEN1044 with the recommended dose from the escalation.

As a routine precaution, subjects dosed with GEN1044 must be monitored during infusion and treated in an area with resuscitation equipment and emergency agents. For weekly dosing during Cycle 1 and Cycle 2, all subjects must be observed for at least 4 hours after ending infusion of GEN1044. For all subsequent cycles, subjects must be observed for at least 2 hours after ending infusion of GEN1044. See Section 4.2 for additional details regarding when an overnight stay (24 hours in-hospital observation) is required.

Refer to the administration and preparation guideline in the GCT1044-01 IMP Manual for additional guidance on trial drug preparation, handling, and storage.

† or equivalent, including oral dose.

Version: 4.0

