# 7.2 GEN1044 Dose Modification Guidance and Safety Stopping Criteria

#### 7.2.1 Dose Escalation Part

- In the event a subject experiences an AE that meets DLT criteria as outlined in Section 7.1, treatment must be permanently discontinued (unless the subject per investigator's discretion has recovered or is expected to recover and expected to benefit from continued treatment). GEN1044 should also be held for the following:
  - If platelet count  $<50\times10^9$ /L, hold dose until platelet count is  $\ge50\times10^9$ /L.
  - If febrile neutropenia  $<0.5\times10^9$ /L, hold dose until neutrophil count is  $\ge0.5\times10^9$ /L.
  - o If hemoglobin is  $\leq 8 \text{ g/dL}$  ( $\leq 5 \text{ mmol/L}$ ), hold dose until hemoglobin  $\geq 8 \text{ g/mL}$  ( $\geq 5 \text{ mmol/L}$ ).
  - **Note**: Transfusion with blood products and/or administration with G-CSF is permitted if needed (see Section 6.5.2.2).
- During the trial, a planned dose of GEN1044 can be postponed for up to 6 weeks for an AE, whether it is considered drug-related or not; a delay of >6 weeks requires permanent discontinuation of treatment. The delay might be extended to 12 weeks after consultation with the sponsor medical monitor.
- First episodes of cytokine blockade-refractory grade 3 CRS or ICANS (see Section 10.4.1) lasting >72 hours require permanent discontinuation from trial treatment.
- First episodes of refractory grade 4 CRS or ICANS require permanent discontinuation from trial treatment.
- Refer to Appendix 7, Table 27, for dose modification guidelines for specific adverse events. For dose escalation, these rules will only apply after the DLT period.

Version: 4.0

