# 9.4.1 Clinical Safety Laboratory Tests

Analysis of the tests detailed in Table 15 will be performed according to the visit schedule outlined in Table 1 (Dose Escalation) and Table 5 (Expansion). **Note**: After laboratory results are available from the Dose Escalation part, the number of laboratory analytes (Table 15) in the Expansion part of the study may be reduced, if the sponsor determines not all these tests are needed.

The investigator must review all laboratory results, document this review, and record any clinically relevant changes including dose modifications or delays as an AE.

Version: 4.0

Table 15 Protocol-Required Safety Laboratory Assessments

Laboratory Assessments	Parameters			
Hematology (local laboratory)	Hematocrit Hemoglobin Mean platelet volume (MPV) Platelet Count RBC Count	noglobin Mean MCV Neutrophils elet volume (MPV) MCH Lymphocytes elet Count MCHC Monocytes		ifferentiala
Biochemistry (local laboratory)	Albumin	Blood Urea Nitrogen (BUN)	Gamma glutamyl transferase (GGT)	Phosphate
`	Alanine aminotransferase (ALT)	Calcium	Glucose	Potassium Sodium
1	Alkaline phosphatase	Chloride	Glycosylated hemoglobin	Total and direct bilirubin
	Amylase	C-reactive Protein	Lactate dehydrogenase (LDH)	Total protein
1	Aspartate Aminotransferase (AST)	Creatinine (estimated GFR by Cockroft-Gault formula)	Lipase Magnesium	Uric acid
Coagulation factors (local laboratory)	Prothrombin time (PT)	International normalized ratio (INR)	Activated partial thromboplastin time (aPTT)	
Urinalysis (local laboratory)	Leukocytes	Protein	Urine pregnancy	
Other screening tests (central laboratory)	Serum beta-hCG b Hepatitis B testing: Antibodies to hepatitis B surface antigen (anti-HBs), antibodies to hepatitis B core antigens (anti-HBc), hepatitis B surface antigen (HBsAg) Triiodothyronine (T3) and thyroxine (T4)			
Additional tests for subjects with prostate cancer (central laboratory)	Prostate-specific antigen Serum testosterone – at S	(PSA)		

a. WBC differential in either absolutes or percents.

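### Section 9.4 requires hematology and biochemistry before every GEN1044 dose, but the visit schedule omits them for 4 of the 12 doses in Cycles 1–4 (C3D8, C3D15, C4D8, C4D15)

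*Protocol*

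**What the plan says.** Protocol Section 9.4 states that biochemistry and hematology values "must be obtained and reviewed by the investigator prior to each GEN1044 administration". The stated purpose is to confirm that the subject can be dosed under the protocol's dosing instructions. The next paragraph changes the timing: "Beginning with Cycle 3, local and central laboratory samples should be obtained on Day 1 of each cycle", or in the three days before it.

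Section 9.4.1 makes Table 1 (escalation) and Table 5 (expansion) the visit schedule for the safety laboratory tests. In both tables, the Cycle 3–4 block marks hematology and biochemistry on Day 1 only. Footnote e, attached to those marks, reads in Table 5: "Starting with C3, obtain labs ≤3 days before D1". Footnote e of Table 1 gives the same timing.

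Dosing is weekly through Cycle 4 (Section 6.3). Both tables mark GEN1044 on Days 1, 8 and 15 of Cycles 3 and 4.

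On extra testing, Section 1.3 says "it may be necessary to perform some of the assessments at unscheduled time points if deemed clinically necessary by the investigator", and the laboratory rows carry the note "At Unscheduled visit, only if relevant".

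**The concern.** The rule and the schedule that is meant to carry it out disagree. A site working from the schedule gives the Day 8 and Day 15 doses of Cycles 3 and 4 without the laboratory check that Section 9.4 makes mandatory. A site working from Section 9.4 has to add draws that the schedule does not show. The protocol does not say which takes precedence.

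Several dosing rules depend on these values. Section 7.2.1 says "GEN1044 should also be held for the following" and lists thresholds for platelets, for neutrophils in febrile neutropenia, and for hemoglobin. Table 27 adds withhold and stop rules for transaminases, bilirubin, platelets and neutrophils. In escalation, Table 27 applies only after the DLT period, so it is in force in Cycles 3–4. Section 7.2.2 holds expansion doses for drug-related events of grade 2 or higher, some of which are laboratory findings.

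Low platelets, afebrile neutropenia and raised transaminases can be silent. Vital signs and adverse event review are scheduled on these days but show neither counts nor liver values. Several Table 27 actions also differ between a first and a second occurrence, so a missed episode can change what is required at the next one.

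**Working it through.** The plan gives no figure of its own on this point. The check is a count from the schedule tables.

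**Doses against scheduled tests** (same result in Tables 1 and 5, and for hematology and biochemistry alike)

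| Cycle | GEN1044 days | Dosing days with both tests marked | Dosing days without |
|---|---|---|---|
| 1 | 1, 8, 15 | 1, 8, 15 | none |
| 2 | 1, 8, 15 | 1, 8, 15 | none |
| 3 | 1, 8, 15 | 1 | 8, 15 |
| 4 | 1, 8, 15 | 1 | 8, 15 |
| 5 onward | 1 | 1 | none |

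Doses in Cycles 1–4: 4 × 3 = 12. Covered: 6 + 2 = 8. Not covered: 12 − 8 = 4, and 4/12 = 33%.

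**Age of a reused Day 1 result.** Section 9.4 sets no limit on sample age. Assume that Day 1 is given on its nominal day, that the sample is drawn 0 to 3 days earlier (footnote e), and that the visit windows are those in the tables (Day 8: +1 day in Table 1, +3 days in Table 5; Day 15: +3 days in both).

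- Day 8, escalation: 7 days to 7 + 3 + 1 = 11 days.
- Day 8, expansion: 7 days to 7 + 3 + 3 = 13 days.
- Day 15, both parts: 14 days to 14 + 3 + 3 = 20 days.

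**Rules that need one of these values**

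- Section 7.2.1: 3 of 3 hold thresholds.
- Table 27, all rows: CRS/ICANS 2, AST/ALT or bilirubin 5, platelets 2, neutropenia 4, febrile neutropenia 2, nausea/vomiting 4, diarrhea 4, other non-hematologic 3. Total 26.
- Table 27, laboratory-dependent rows: 5 + 2 + 4 + 2 = 13.

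**DLT period.** Under Section 7.1 it ends at Day 21 of Cycle 1, or at C2D7 with two intermediate doses. Every dosing day of Cycles 1–2 has both tests marked, so the gap lies wholly after it.

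**The case against.** The strongest reply is that the safeguard already exists. Section 9.4 is mandatory, the tables leave out marks but forbid nothing, and the Day 1 wording can be read as a sampling window for the Day 1 draw. On that reading a site that skips laboratory tests at C3D8 simply breaches Section 9.4, and the defect is four missing marks. It is also fair that the unscheduled-visit note governs a different column, and that a Day 1 result does precede the Day 8 dose in time.

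Part of this stands. The tables do not prohibit testing, and a site can comply with Section 9.4 by adding draws. But Section 9.4.1 sends sites to the tables, and the Cycle 3 sentence and both footnotes repeat the Day 1 timing. The provisions for extra testing leave it to the investigator's judgment and do not turn it into the required check. Reusing a Day 1 value fits poorly with a rule written for each administration, given that Cycles 1–2 schedule both tests on every dosing day.

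The reach is also limited. The 33% describes a subject who receives all 12 doses. The documents do not say how many subjects were dosed beyond C3D1, and SAP Section 1.2 records that enrollment was stopped after the safety review of 29 September 2021. Fever is clinically visible; leaving febrile neutropenia out gives 2 of 3 thresholds and 13 − 2 = 11 of 26 rows. Confirming febrile neutropenia still needs a neutrophil count, so the fuller figures are kept here.

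**Conclusion.** The concern holds. Four of the 12 doses in Cycles 1–4 have no hematology or biochemistry scheduled for them, although Section 9.4 requires both before each dose. The count is exact for both tables. The result ages of 7 to 20 days apply only if a site reuses the Day 1 sample, and they assume Day 1 is given on its nominal day.

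This is a subject-safety and conduct issue that should be fixed. It does not bias any analysis. DLT assessment and mBOIN decisions are untouched, Cycles 1–2 and Cycle 5 onward are consistent, and SAP Section 2.2 states that no expansion data was collected. The practical reach is escalation subjects dosed on Day 8 or 15 of Cycle 3 or 4.

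**What to change.** Mark local hematology and biochemistry on Days 8 and 15 of Cycles 3 and 4 in Tables 1 and 5. Amend footnote e of both tables and the Cycle 3 sentence in Section 9.4 so that the pre-dose check is scheduled for every dose. Scheduled coverage then goes from 8 of 12 to 12 of 12 doses, and it becomes clear that a missing Day 8 or Day 15 result is a deviation.

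The cost is edits to two tables, two footnotes and one sentence, plus four local blood draws per subject who completes Cycle 4. The draws fall at existing infusion visits, and Section 9.4 already requires these tests before each dose.

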# 9.4.1 Clinical Safety Laboratory Tests

Analysis of the tests detailed in Table 15 will be performed according to the visit schedule outlined in Table 1 (Dose Escalation) and Table 5 (Expansion). **Note**: After laboratory results are available from the Dose Escalation part, the number of laboratory analytes (Table 15) in the Expansion part of the study may be reduced, if the sponsor determines not all these tests are needed.

The investigator must review all laboratory results, document this review, and record any clinically relevant changes including dose modifications or delays as an AE.

Version: 4.0

Table 15 Protocol-Required Safety Laboratory Assessments

Laboratory Assessments	Parameters			
Hematology (local laboratory)	Hematocrit Hemoglobin Mean platelet volume (MPV) Platelet Count RBC Count	noglobin Mean MCV Neutrophils elet volume (MPV) MCH Lymphocytes elet Count MCHC Monocytes		ifferentiala
Biochemistry (local laboratory)	Albumin	Blood Urea Nitrogen (BUN)	Gamma glutamyl transferase (GGT)	Phosphate
`	Alanine aminotransferase (ALT)	Calcium	Glucose	Potassium Sodium
1	Alkaline phosphatase	Chloride	Glycosylated hemoglobin	Total and direct bilirubin
	Amylase	C-reactive Protein	Lactate dehydrogenase (LDH)	Total protein
1	Aspartate Aminotransferase (AST)	Creatinine (estimated GFR by Cockroft-Gault formula)	Lipase Magnesium	Uric acid
Coagulation factors (local laboratory)	Prothrombin time (PT)	International normalized ratio (INR)	Activated partial thromboplastin time (aPTT)	
Urinalysis (local laboratory)	Leukocytes	Protein	Urine pregnancy	
Other screening tests (central laboratory)	Serum beta-hCG b Hepatitis B testing: Antibodies to hepatitis B surface antigen (anti-HBs), antibodies to hepatitis B core antigens (anti-HBc), hepatitis B surface antigen (HBsAg) Triiodothyronine (T3) and thyroxine (T4)			
Additional tests for subjects with prostate cancer (central laboratory)	Prostate-specific antigen Serum testosterone – at S	(PSA)		

a. WBC differential in either absolutes or percents.

